1.4. Objectives of the study

Based on the above introduction and study question, the objectives can be classified into general and specific as follows:

General objective

The overall purpose of this study is to compare the efficacy of serratiopeptidase and escin in the reduction of post-operative complications (i.e., pain, trismus, and facial

swelling) following impacted third molar surgery, when both used in addition to conventional drugs.

Specific objective

1. Evaluate the efficacy of serratiopeptidase, when used in addition to conventional drugs, in reducing post-operative pain, trismus, and facial swelling following impacted third molar surgery.
2. Evaluate the efficacy of escin, when used in addition to conventional drugs, in reducing post-operative pain, trismus, and facial swelling following impacted third molar surgery.

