1.5. Study Hypotheses

Based on the study main problem, objectives, and literature review, three main hypotheses are constructed in order to test the relationship between the study variables.

These hypotheses are listed in this section as follows:

1. There is a statistically significant difference in serratiopeptidase, when used in addition to conventional drugs, in reducing post-operative pain, trismus, and facial swelling compared to conventional drugs alone following impacted third molar surgery.
2. There is a statistically significant difference in escin, when used in addition to conventional drugs, in reducing post-operative pain, trismus, and facial swelling compared to conventional drugs alone following impacted third molar surgery.
3. There is a statistically significant difference in serratiopeptidase in reducing post-operative pain, trismus, and facial swelling compared to escin, when

both used in addition to conventional drugs, following impacted third molar surgery.

Chapter 2:

Literature Review

2.1.Impacted Third Molar

The third molars, commonly known as wisdom teeth, often lead to complications during eruption, presenting a frequent concern in oral surgery (Wray et al., 2003). (Lytle, 1979) defines an impacted tooth as “*a tooth that has failed to erupt into its normal functional position beyond the time usually expected for such appearance. Eruption may have been prevented by adjacent hard or soft tissue including tooth, bone, or dense soft tissue*”. Among impacted teeth, mandibular third molars are the most common, followed by maxillary third molars and maxillary canines. Most unerupted teeth are extracted due to pain or infection, but other reasons include involvement in pathologies like cysts or tumors, causing resorption of adjacent teeth, or interfering with surgical procedures (Undrell Moore, 2011).

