3.1. Study Design

This clinical trial will utilize a split-mouth design, randomly assigning two different treatments to each half of the patient's mouth. From this randomized study which is characterized by a triple-blind study, the procedures are going to be performed by qualified and experienced professional. However, the operator will have no access to data evaluated. The evaluator will have access to all responses of the symptoms of patients and will not know the treatment that is going to be selected, while the patient is unaware of which treatment or intervention is being applied to each side of their mouth. This stringent blinding approach minimizes potential biases and significantly enhances the scientific validity of the study.

Patients will be assigned into two groups and each patient acted as their own control using the split-mouth technique. One impacted third molar will be removed from one side and will receive conventional drugs while the other side will be removed after 3 weeks (wash-out period) and receive additional treatment beside the conventional drugs (i.e., either enzyme or herbal). The two groups will be classified as follows:

- The first group will receive conventional drugs with 10mg oral serratiopeptidase at immediate post-operative time and three times a day for post-operative five days on the first surgical visit and on the second surgical visit (after 3 weeks) conventional drugs will be given only or vice versa.
- The second group will receive conventional drugs with 20mg oral escin at immediate post-operative time and three times a day for post-operative five days on the first surgical visit and on the second surgical visit (after 3 weeks) conventional drugs will be given only or vice versa.

The conventional drugs, it will be administered to patients in the two groups, includes: Amoxicillin 500mg Cap b.i.d., Metronidazole 500mg Tab t.i.d., Diclofenac sodium 50mg Tab b.i.d.

3.2.Study Population

The study population will include patients who will visit the dental clinics in the College of Dentistry, University of Science and Technology, Yemen (USTY) for impacted mandibular third molars extraction during 2024.

3.3.Sample Size

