The sample size is the number of participants planned to be included in the trial, usually determined using a statistical power calculation (Zanatta et al., 2017). This study determined the sample size using a power calculation based on previous research by (Costa et al., 2015). Their study found that preemptive use of etoricoxib 120mg significantly reduced the need for rescue analgesic medication compared to a placebo (1.6 ± 1.3 vs 4.0 ± 2.5). To achieve a power of 80% and a confidence interval of 95%. The study will need to evaluate 11 surgical sites per sub-group (<http://www.openepi.com/SampleSize/SSMean.htm>). To account for a potential 20% drop-out rate, a total of 14 sites per sub-group will be recruited. This will result in a total sample size of 56 dental units (2 teeth per patient) from 28 patients. The following Table 3-1 illustrates the study sample size and the planned treatment.

Table 3-1 : Sample Size and Study Treatment.

Groups	I		II		Total
Patients	14		14		28
Sub-groups	Control 1	Study 1	Control 2	Study 2	4
Sample size	14	14	14	14	56
Conventional Treatment	Amoxicillin 500mg Cap b.i.d		Metronidazole 500mg Tab t.i.d		N/A
	Diclofenac sodium 50mg Tab b.i.d				
Study Treatment	N/A	Serratiopeptidase 10mg t.id	N/A	Escin 20mg t.id	N/A

3.4.Sample Selection

Patients who will undergo to surgical removal of the impacted third molar will be assessed for their eligibility to participate according to the following inclusion and exclusion criteria:

Inclusion criteria:

- Medically fit patients.
- The presence of two asymptomatic mandibular third molar indicated for surgical extraction.
- Absence of pericoronitis or signs of inflammation during the last 30 days

Exclusion criteria:

- Patient administered other drugs such as NSAIDS and steroids.
- Patient has allergy to the drugs used in this study.
- Pregnant patient or a patient with lactation.
- Immunocompromised patients with diabetic or hypertension (from patient's history).
- Patients with irradiated maxillofacial region.
- Intellectually disabled patients and patients unable to come for follow up visits.
- Patients with acute and subacute pericoronitis

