3.5. Randomization

This clinical trial will utilize simple randomization based on the technique described by (Oliveira et al., 2021). This method involves drawing envelopes to determine the following:

- Surgical site: Test or control side
- Tooth: Right third molar ("A") or left third molar ("B")
- Surgery order: First or second session

The following steps of randomization will be followed:

1. Draw the tooth: An envelope is drawn to determine which third molar will be extracted first (right or left).
2. Draw the intervention: A second envelope is drawn to determine whether the selected tooth will receive the test intervention ("X-1") or no intervention ("X-2").
3. Draw the surgery order: A final envelope is drawn to determine whether the selected tooth will be extracted in the first or second surgery session.

3.6.Pre-operative and Post-operative Assessment

Prior to surgical removal of impacted third molar, preoperative variables (i.e., pain, trismus, and facial swelling) will be taken for each patient and recorded in the data collection sheet. Furthermore, the same post-operative variables (preoperative variables) will be taken immediately after the procedure, 2nd day, 3rd day and 5th day after the operation. Both pre-operative and post-operative variables will be done by the same measurements.

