3.7. Surgical Procedures

To minimize variability and bias, all surgical extractions will be performed by the same oral surgeon utilizing a uniform technique (Isola et al., 2019). Each patient will receive similar operative procedures under identical conditions, including administration of local anesthetic consisting of inferior alveolar, lingual, and long buccal nerve blocks. Additionally, the same surgical procedure will be adopted for all groups. Access to the third molar will be achieved from the buccal aspect. A mucoperiosteal flap will be raised, and bone removal with a round bur in a straight handpiece under continuous irrigation with a sterile saline solution and/or tooth sectioning will be performed. After tooth extraction, the alveolus will be inspected, curetted for granulation tissue removal, and irrigated with a sterile saline solution. The surgical wound will be closed using a 4–0 reabsorbable suture (Coated VICRYL). This meticulous approach minimizes intraoperative trauma and ensures consistency across all groups.

Post-operatively, patients will receive their assigned medications and receive thorough instructions regarding dietary restrictions (liquid and cold diet for 24 hours), oral hygiene practices, and avoidance of mouthwashes to prevent bleeding. They will be informed about potential complications and instructed to contact the surgeon if any issues arise. Additionally, they will be requested to report any physical symptoms experienced during the study period.

3.8.Ethical Consideration

The ethical approval will be obtained from the USTY Medical Research Ethics Committee. The purpose and methodology of the study will be explained to all the participants. Hence, a participant information sheet (Appendix B) will be given to all participants and a written informed consent form (Appendix C) will be obtained from them with the tenets of the revised Declaration of Helsinki 1975.

3.9.Statistical Method

Quantitative data (pain, trismus, and facial swelling) will be expressed as means and standard deviations and compared using the paired t test (parametric) or Wilcoxon test (nonparametric). The Shapiro–Wilk test will be used to verify the normality of the data. A difference of $P < .05$ will be considered statistically significant. The data analysis will be performed using SPSS V.25 (SPSS, JASP).

References

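### The only power calculation is for rescue-analgesic need, which the trial does not plan to analyse, and nothing sizes or tests serratiopeptidase against escin

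*Combined protocol and SAP*

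**What the plan says.** Section 3.3 holds the only power calculation. It relies on a study in which pre-emptive etoricoxib 120 mg "significantly reduced the need for rescue analgesic medication compared to a placebo", with figures of 1.6 ± 1.3 versus 4.0 ± 2.5. From 80% power and 95% confidence it concludes: "The study will need to evaluate 11 surgical sites per sub-group". Allowing for 20% drop-out, "a total of 14 sites per sub-group will be recruited", giving 28 patients and 56 teeth.

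Section 3.6 lists what is measured: "preoperative variables (i.e., pain, trismus, and facial swelling) will be taken for each patient", and the same three variables are taken again after surgery. Section 3.9 says these three outcomes are "compared using the paired t test (parametric) or Wilcoxon test (nonparametric").

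Section 1.4 gives the general objective: "The overall purpose of this study is to compare the efficacy of serratiopeptidase and escin in the reduction of post-operative complications". Hypothesis 3 in section 1.5 repeats it formally: "There is a statistically significant difference in serratiopeptidase in reducing post-operative pain, trismus, and facial swelling compared to escin". Section 3.1 sets the structure: "Patients will be assigned into two groups and each patient acted as their own control using the split-mouth technique". One group receives serratiopeptidase and the other escin, each at one of the patient's two surgeries.

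**The concern.** A power statement is useful only for the endpoint, contrast and test it was computed for. Here none of the three carries over.

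- **Endpoint.** The calculation uses rescue-analgesic need. Outside section 3.3, rescue use does not appear in the objectives, hypotheses, assessments, statistical method or case sheet (Appendix A). The patient's own form is described in section 3.6.1 as holding pain scores. Means and SDs of rescue need say nothing about centimetres of VAS or millimetres of mouth opening.
- **Contrast.** The source compares an active drug with placebo. This trial compares add-on with no add-on within patients, and two active add-ons between patients.
- **Test.** The stated 11 matches a formula for two independent means. The planned test is paired, and no within-patient correlation is given.

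The larger gap is the drug-versus-drug question. Each patient receives only one of the two add-ons, so the comparison is between patients. A paired t test cannot address it, and no number of patients is derived for it. The reader cannot tell what difference the trial could detect on its stated overall purpose, so a non-significant result there could be taken to mean that the drugs are equivalent.

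**Working it through.** **1. Reproduce the plan's figure.** Inputs from section 3.3: means 1.6 and 4.0 (difference 2.4), SDs 1.3 and 2.5, 80% power, 95% confidence read as two-sided 5%.

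n = (1.3² + 2.5²)(1.960 + 0.842)² / 2.4² = 10.82, rounded up to 11. Drop-out: 11 / 0.8 = 13.75, rounded up to 14. Both figures reproduce.

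**2. The same inputs under the planned paired test.** SD of the difference = √(1.3² + 2.5² − 2ρ × 1.3 × 2.5). The correlation ρ is an assumption, as the plan gives none. Power is from the noncentral t distribution.

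| ρ | SD of difference | Effect in SDs | Power, 11 pairs | Power, 14 pairs |
|---|---|---|---|---|
| 0 | 2.818 | 2.4 / 2.818 = 0.85 | 72% | 84% |
| 0.5 | 2.166 | 2.4 / 2.166 = 1.11 | 91% | 97% |

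With 11 pairs, 80% is reached only if ρ is at least about 0.21. These powers still refer to rescue need, not to a planned outcome.

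**3. What the planned numbers can detect.** The plan has no target difference or SD for pain, mouth opening or swelling, so the answer must be in SDs of the within-patient difference (two-sided 5%, 80% power). The between-drug rows apply a two-sample t test to those differences, with equal SDs assumed.

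| Comparison | 14 per group | 11 per group |
|---|---|---|
| Add-on vs control, paired t | 0.81 SD | 0.94 SD |
| Serratiopeptidase vs escin, two-sample t | 1.10 SD | 1.26 SD |
| Ratio | 1.36 | 1.34 |
| Between-drug 95% CI half-width, t × √(2/n) | 0.78 SD | 0.89 SD |

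**4. Power for Hypothesis 3.** The true differences are illustrations only.

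| True difference | 14 vs 14 | 11 vs 11 |
|---|---|---|
| 0.5 SD | 25% | 20% |
| 0.8 SD | 53% | 43% |

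**5. In VAS units.** Assume the SD of the paired pain difference lies between 1.5 and 3.0 cm. Multiplying the step 3 figures by 1.5 and 3.0:

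- within patients: 1.2 to 2.4 cm (14 pairs), 1.4 to 2.8 cm (11 pairs);
- between drugs: 1.7 to 3.3 cm (14 vs 14), 1.9 to 3.8 cm (11 vs 11).

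**6. If alpha were split over the three outcomes** (an assumption; the plan has no adjustment), at 0.05/3 the detectable differences become 0.97 and 1.14 SD within patients, and 1.30 and 1.49 SD between drugs, for 14 and 11 per group.

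**The case against.** Borrowing inputs from a similar trial is ordinary practice, and the source was itself a split-mouth, triple-blind third-molar study. Nor do the documents show that Hypotheses 1 and 2 are underpowered. The borrowed effect, 0.85 SD at zero correlation, is close to the 0.81 SD detectable with 14 pairs, and positive correlation would help. This stands, with one qualification: with the 11 evaluable pairs the plan counts on, the detectable difference is 0.94 SD, so the borrowed effect falls short at zero correlation. The endpoint mismatch alone would therefore be a modest fault; the weight rests on the between-drug comparison.

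On that comparison, three things can be said for the plan.

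- Both specific objectives in section 1.4 are within-patient, and no equivalence claim is planned. True, but the same section makes the drug comparison the overall purpose, and section 1.5 makes it a formal hypothesis.
- Wilcoxon could mean the rank-sum test. Beside a paired t test, signed-rank is the natural reading. On either reading, no parametric between-group test, no analysed quantity and no power is given.
- The effect sizes in steps 4 and 5 are the reviewer's. They are, because the plan offers none, and underpowering against a target cannot be shown without a target. The detectable differences in step 3 do not depend on them.

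Two limits remain. The patient pain form is not reproduced, so the absence of rescue recording is established for the case sheet and for sections 3.6 to 3.9, not for that form. Also, the envelope draws in section 3.5 settle tooth, intervention and order, but not which drug group a patient joins. That is a separate issue, but it affects how much a between-drug test can bear.

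**Conclusion.** The concern holds and must be fixed. The stated 80% power attaches to no planned test, and the trial's overall purpose has neither a sample-size basis nor a test that clearly fits it. The arithmetic behind 11 and 14 is correct.

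For Hypotheses 1 and 2 the consequence is modest: the power is unstated rather than shown to be low. For Hypothesis 3 it is serious. The detectable difference is about 1.35 times the within-patient one, which at 14 per group exceeds even the whole borrowed drug-versus-placebo effect at zero correlation (1.10 against 0.85 SD).

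The SD-unit results assume two-sided 5% t tests and, between drugs, equal SDs of the within-patient differences. The VAS figures also assume an SD of 1.5 to 3.0 cm.

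**What to change.** Keep 28 patients and withdraw the 80% claim based on rescue analgesia.

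- **Section 3.3, replace with:** *With 14 patients per group (11 after 20% drop-out), a two-sided 5% paired t test has 80% power for a within-patient difference of 0.81 SD (0.94 SD) of the paired difference in [one measured outcome and day, for example pain VAS on the 2nd day]. The SD of the paired difference is assumed to be [value], from an outcome SD of [value] and a correlation of [value]. No multiplicity adjustment is included. The comparison of serratiopeptidase with escin, on within-patient differences with equal SDs assumed, has 80% power only for about 1.10 SD (14 vs 14) to 1.26 SD (11 vs 11).*
- **Section 3.9, add:** *Serratiopeptidase and escin are compared on each patient's difference between add-on and control sessions, by two-sample t test (or Mann-Whitney test), with a 95% confidence interval.*
- **Section 1.5, Hypothesis 3, add:** *This is tested on the between-group difference in within-patient differences; a non-significant result will not be read as equivalence.*

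The sponsor should also say why a between-drug difference of that size is plausible or, failing that, label the comparison exploratory. Section 3.5 should state how patients are allocated to the two drug groups.

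The cost is rewording: no extra patients, visits or data fields. The stated power becomes less favourable, especially for the general objective, and the sponsor must commit to one outcome and day with a stated SD and correlation.

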1.1. Background

The surgical removal of impacted third molars, commonly known as wisdom teeth, remains a frequent procedure in oral and maxillofacial surgery. While the procedure itself is routine, it often leads to undesirable post-operative complications such as pain, trismus (limited jaw opening), and facial swelling (Al-Khateeb & Nusair, 2008; Brković et al., 2017). These complications arise from the natural inflammatory response triggered by the surgical trauma.

Traditionally, the management of these complications has relied on pharmacological interventions, primarily corticosteroids and nonsteroidal anti-inflammatory drugs (NSAIDs) (Kaplan & Eroğlu, 2016). These medications offer potent anti-inflammatory and analgesic properties, effectively reducing pain and swelling. However, their use is often associated with undesirable side effects, including gastrointestinal bleeding, renal dysfunction, and blood dyscrasias, raising concerns regarding their long-term safety (Piecuch, 2012). Recognizing these limitations, researchers have explored alternative therapies with potentially fewer side effects. Among these promising alternatives are therapeutic enzymes and phytotherapeutic drugs derived from natural sources.

Serratiopeptidase, a proteolytic enzyme, has emerged as a potential candidate for managing post-surgical inflammation. Studies have shown its effectiveness in reducing inflammation around teeth and dental implants, suggesting its potential benefit after third molar extraction (Sannino et al., 2013; Villafuerte-Nuñez et al., 2013). However, existing research in this area remains limited, particularly regarding its efficacy in managing post-operative complications following third molar teeth removal.

Similarly, phytotherapeutic drugs offer a promising avenue for post-surgical pain and swelling management. These natural extracts have demonstrated their effectiveness

in treating various inflammatory conditions and postsurgical complications (Olmedo-Gaya et al., 2016; Pavan et al., 2012). Notably, studies have shown their ability to reduce pain and discomfort after third molar surgery, highlighting their potential as safe and effective therapeutic options (Isola et al., 2019). One such phytotherapeutic drug, escin, derived from horse chestnut, has exhibited potent anti-inflammatory activity, suggesting its potential benefit in reducing post-surgical inflammation and swelling (Wang et al., 2009).

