3.6.1. Assessment of Pain

Measurements of this outcome will consider pain intensity based on Figure 3-1. Preoperative and postoperative pain intensity will be assessed using a standardized 10-centimeter visual analogue scale (VAS), ranging from 0 (no pain) to 10 (worst possible pain) (Sirintawat et al., 2017). Prior to surgery, patients will receive thorough instructions on using the VAS to accurately self-report their pain. Following the procedure, they will record their pain scores on a standardized form and return it to the researcher on the day of suture removal, allowing for continuous monitoring and evaluation of pain management effectiveness (Costa et al., 2015).

[figure not shown]

Figure 3-1 Pain Intensity Measurement.

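### The 80% power is computed from rescue analgesic use in another trial and is not established for any outcome of this one; state detectable differences instead

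*Combined protocol and SAP*

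**What the plan says.** Section 3.3 takes its inputs from an earlier split-mouth trial in which pre-emptive etoricoxib 120 mg "significantly reduced the need for rescue analgesic medication compared to a placebo", with values of 1.6 ± 1.3 and 4.0 ± 2.5. It asks for 80% power and 95% confidence, uses a web calculator for comparing means, and concludes: "The study will need to evaluate 11 surgical sites per sub-group". A 20% drop-out allowance raises this to 14 per sub-group, which makes 28 patients and 56 teeth.

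The outcomes are different ones. The objectives (1.4) and hypotheses (1.5) name pain, trismus and facial swelling. Section 3.6 measures these before surgery, and "the same post-operative variables (preoperative variables) will be taken immediately after the procedure, 2nd day, 3rd day and 5th day after the operation". Section 3.9 analyses the same three: "Quantitative data (pain, trismus, and facial swelling) will be expressed as means and standard deviations and compared using the paired t test", or the Wilcoxon test. The Appendix A case sheet has rows for these three only.

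On medication, the conventional drugs given in both sessions include "Diclofenac sodium 50mg Tab b.i.d" (3.1). No rescue drug is named. Section 3.4 excludes patients who were given other drugs such as NSAIDs and steroids. For pain, patients complete a separate form: "they will record their pain scores on a standardized form and return it to the researcher on the day of suture removal" (3.6.1). Section 3.8 adds that "a participant information sheet (Appendix B) will be given to all participants". Neither that form nor Appendix B was available for this review.

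**The concern.** A power statement belongs to one outcome, one contrast and one test. Here the outcome (rescue analgesic use), the contrast (a COX-2 inhibitor against placebo) and the formula (independent samples) all come from outside the planned analysis. If VAS pain, mouth opening or swelling turns out non-significant, a reader of 3.3 may take it as a negative result from a trial with 80% power for that outcome. The plan does not establish this.

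A secondary matter follows. The source trial treated rescue analgesic use as something that differed between treatments, but no visible page of this plan records analgesics taken beyond the study regimen. Section 1.1 says of corticosteroids and NSAIDs: "These medications offer potent anti-inflammatory and analgesic properties, effectively reducing pain and swelling". If patients took more extra analgesics in control sessions, the pain difference would shrink, and so might the swelling difference if the extra drug were an NSAID. More use in test sessions would act the other way. Intake not written down at the time cannot be reliably recovered later.

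**Working it through.** **Inputs.** From 3.3: means 1.6 and 4.0, SDs 1.3 and 2.5, power 80%, confidence 95% (read as two-sided 0.05; sidedness is not stated), drop-out 20%. From 3.9: paired t test, significance level 0.05. From Table 3-1: 14 patients in each of two groups.

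**1. The plan's own figure.** For two independent means with the normal approximation:

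n = (1.960 + 0.842)² × (1.3² + 2.5²) / (4.0 − 1.6)² = 7.849 × 7.94 / 5.76 = 10.82, so 11.

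Drop-out: 11 / 0.8 = 13.75, so 14. Both match 3.3. By the same formula, power is 80.6% at 11 and 89.0% at 14. The 80% thus comes from the rescue-analgesic contrast under an independent-samples formula.

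**2. The same contrast under the planned paired test.** The SD of the within-patient differences is √(1.3² + 2.5² − 2r × 1.3 × 2.5) = √(7.94 − 6.5r), where r is the within-patient correlation. The documents do not give r, so a range is shown (noncentral t, two-sided 0.05).

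| Assumed r | SD of differences | 2.4 / SD | Power, 11 pairs | Power, 14 pairs |
|---|---|---|---|---|
| 0 | 2.82 | 0.85 | 72% | 84% |
| 0.3 | 2.45 | 0.98 | 83% | 92% |
| 0.5 | 2.17 | 1.11 | 91% | 97% |

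With 11 pairs, 80% is reached at about r = 0.21. The table also assumes that the 2.4 difference carries over to this trial, which step 5 questions.

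**3. What the planned paired test can detect (hypotheses 1 and 2).** Solving the noncentral t for 80% power gives 0.938 SD of the within-patient differences with 11 pairs and 0.810 SD with 14. For a difference of 0.5 SD, power is 32% and 41%.

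The documents give no SD for VAS pain. Under an assumed SD of differences of 1.5, 2.0 or 2.5 cm:

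- 11 pairs: 0.938 × SD = 1.4, 1.9 or 2.3 cm
- 14 pairs: 0.810 × SD = 1.2, 1.6 or 2.0 cm

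**4. Serratiopeptidase against escin (hypothesis 3).** Each patient receives only one of the two drugs, so this comparison is between patients. Section 3.9 names no test for it; a two-sample t test is assumed. The detectable difference at 80% power is about 1.26 SD with 11 per group and 1.10 SD with 14, in SD units of whatever patient-level score is compared.

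**5. Does the source contrast carry over?** The cited difference is an active anti-inflammatory against placebo. Here both sessions include scheduled diclofenac, and the contrast is the addition of serratiopeptidase or escin. Nothing in the documents supports a difference of 2.4 in extra analgesic use under those conditions. It may be smaller.

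**The case against.** Section 3.3 never says in words that the 80% applies to VAS, trismus or swelling, and sizing a trial on a related outcome is common. That is fair, but it does not make the figure apply to those outcomes, and the plan offers no other power statement for them.

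The formula mismatch is mild and may favour the plan. A modest positive correlation (about 0.21) restores 80% with 11 pairs, and 14 pairs give 84% even at r = 0. This stands: the paired design is no weakness in itself. The difficulty is that r is unstated and the outcome is not one the trial analyses.

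A reader might infer that the trial is underpowered. The documents do not support that. They give no expected difference or SD for the three outcomes, so power for them can be neither confirmed nor denied. A reader might also think it enough to restrict the 80% to rescue analgesic use. That would still credit this trial with power it has not shown, for the reasons in steps 2 and 5.

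On the log, it is tempting to conclude that extra analgesics go unrecorded and bias the pain result. Neither part is shown. The patient pain form and Appendix B may contain a field or a rule, and no visible text shows that use will be unequal. The exclusion of patients given other NSAIDs bears on this, but it is an entry criterion: it does not clearly govern the five post-operative days, and it records nothing.

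**Conclusion.** The concern holds in this form: the sample-size arithmetic is right, but the 80% reproduces another trial's rescue-analgesic contrast and is not established for any outcome of this one. What the planned numbers support is detection, with 80% power, of 0.94 SD (11 pairs) or 0.81 SD (14 pairs) for each drug against control, and of about 1.26 SD or 1.10 SD for one drug against the other. These figures rest on a two-sided 0.05 level, t tests and complete data at the stated number. The centimetre values for VAS rest on assumed SDs. The analgesic log is a lesser point of good practice, and no size of dilution is claimed. Confidence on the log is limited by the pages not available; the power point does not depend on them.

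**What to change.** 1. In 3.3, say that the 80% figure reproduces the cited trial's rescue-analgesic contrast under an independent-samples formula and is not a power statement for any outcome of this trial. Replace it with the detectable differences at 80% power, two-sided 0.05. For hypotheses 1 and 2 (paired): 0.94 SD of the within-patient differences with 11 pairs, 0.81 SD with 14. For hypothesis 3 (between patients): about 1.26 SD at 11 per group, 1.10 SD at 14. The sample size does not change.

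2. As a secondary addition, unless the patient pain form already does this, record on that form and in Appendix A the type, dose and time of any analgesic taken beyond the study regimen, through day 5 of each session. In 3.9, compare within-patient intake between sessions, descriptively or with the paired t or Wilcoxon test, and report it beside the VAS and swelling results.

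The cost is a few sentences in 3.3 and 3.9, one line per day on a form patients already complete, and one row in the case sheet. The downside is a slight extra burden on patients. The log would show unequal use but not correct for it, and it adds no power for the three listed outcomes. What patients may take does not change.
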